## **MATERIALS AND METHODS**

### ***Study Population and Protocol***

This was a single-center, prospective, assessor-blinded, noninferiority, randomized controlled study conducted at a tertiary referral center (Incheon St. Mary's Hospital, Incheon, Korea). Individuals who underwent colonoscopy with or without esophagogastroduodenoscopy (EGD) for various indications were eligible for inclusion. Study subjects were enrolled between November 2017 and February 2018. Individuals who met all of the following criteria were included: (1) age 40–75 years; (2) American Society of Anesthesiologists (ASA) class I or II; (3) outpatients; and (4) no previous history of bowel resection or gastrectomy. Exclusion criteria were as follows: (1) cancellation, (2) violation of protocol for bowel preparation, such as subjects in the SDD group ingesting a purgative the previous day or as an SPD; or subjects in the SPD group ingesting a purgative the previous day or as an SDD. After informed consent was obtained, study subjects were randomly assigned to the SDD or SPD group. Randomization was performed using a block size of four, stratified by colonoscopy time (morning vs afternoon) and sex, using a computer-generated randomization list.

The protocol for bowel preparation is shown in Figure 1. Subjects underwent bowel preparation at home. Study subjects were encouraged to finish 2 L PEG within 1 h. If ingestion was difficult, 2 L PEG was consumed within 1.5 h. Hence, 2 to 3 h were required to fully ingest the 4 L PEG. Individuals in the SDD group ingested PEG on the day of the colonoscopy. For those who underwent morning colonoscopy, ingestion of 4 L PEG was started at 5 a.m. Individuals who were scheduled to undergo afternoon colonoscopy were instructed to take 2 L PEG starting at 7 a.m., then after a 2-h break, the remaining 2 L PEG was ingested starting at 10 a.m. Individuals in the SPD were instructed to begin ingesting 2 L

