### ***Bowel Cleansing Efficacy, Bowel Movement Kinetics, and Colonoscopy Results***

The primary endpoint of this study was the bowel cleansing efficacy assessed by the Boston bowel preparation scale (BBPS). The BBPS score is the sum of three segmental scores (range 0–9). Each segment is graded on a 4-point scale: 0, inadequate; 1, poor; 2, good; and 3, excellent. The rates of cleansing success, defined as all segments  $\geq 2$  and total BBPS score, were compared between groups. The bowel cleansing efficacy was also assessed by the Aronchick scale, which has scores of excellent, good, fair, poor, and very poor; details of the Aronchick scale are described elsewhere.

Bowel movement kinetics included the number of defecations, the start and finish time of bowel preparation, and the last defecation time. The amount of PEG and additional water ingested were recorded.

The results of the colonoscopy were analyzed. The cecal intubation time, colonoscopy withdrawal time, polyp detection rate (PDR), ADR, and the number of adenomas per patient

were recorded. For those who underwent EGD, fluid in the stomach was suctioned and its volume was measured.

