### ***Statistical Analysis***

We assumed a bowel cleansing success rate for SPD of 85% and set the inferior margin at 10%. With 80% power and a type I error of 0.05, the required sample size for each group was calculated to be 158. A total of 176 subjects in each group was required, considering a 10% drop-out rate. Continuous variables are expressed as mean  $\pm$  standard deviation. Categorical variables are expressed as number and percent. The demographic characteristics, bowel cleansing efficacy, safety profile, tolerability, bowel movement kinetics, and results of colonoscopy were compared between the two groups. For this analysis, we used Student's *t* test for continuous variables, and the chi-square or Fisher's exact test for categorical variables. A *p*-value  $<0.05$  was considered significant. The safety analysis of safety and

tolerability included all subjects except those who were excluded for cancellation or protocol violation. Per-protocol (PP) analysis was used for the patients who completed colonoscopy. Bowel cleansing efficacy and bowel movement kinetics were investigated in the PP analysis. All statistical analyses were conducted using SAS software (9.0; SAS Institute, Cary, NC, USA).

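### The primary endpoint is analysed only in patients who completed colonoscopy, with no all-randomised analysis beside it, so the effect of post-randomisation losses on the noninferiority result cannot be judged

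*Combined protocol and SAP*

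**What the plan says.** The section on bowel cleansing efficacy makes cleansing on the Boston scale (BBPS) the primary endpoint, with success meaning a score of at least 2 in every segment. Statistical Analysis states "Per-protocol (PP) analysis was used for the patients who completed colonoscopy" and then "Bowel cleansing efficacy and bowel movement kinetics were investigated in the PP analysis". The only other set described, for safety and tolerability, also leaves out cancellers and violators. No set contains everyone randomised, and there is no rule for a randomised subject without a colonoscopy result.

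Under Study Population and Protocol, the plan says "Exclusion criteria were as follows: (1) cancellation, (2) violation of protocol for bowel preparation". The example of a violation is "such as subjects in the SDD group ingesting a purgative the previous day or as an SPD", with a matching example for SPD. The next sentence reads "After informed consent was obtained, study subjects were randomly assigned to the SDD or SPD group".

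The sample size assumes 85% success in SPD, a 10-point margin, 80% power and a type I error of 0.05. That gives 158 per group, and "A total of 176 subjects in each group was required, considering a 10% drop-out rate".

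**The concern.** A subject can take purgative at the wrong time for the assigned group only after a group has been assigned, so exclusion for this reason necessarily follows randomisation. Cancellation probably does too, although its timing is not stated. Only the colonoscopists are described as blinded; subjects follow a schedule they know, and the two schedules differ. Loss may therefore depend on both arm and outcome.

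The meaning of completing colonoscopy is also undefined. An examination stopped for poor preparation could leave the analysis instead of counting as a failure.

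The planned drop-out of 10% is about 18 of 176 subjects per arm, a fraction as large as the margin. If losses are selective, the contrast among completers is no longer the randomised contrast, and the plan has no second analysis to show whether this happened.

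**Working it through.** **The plan's own figure.** With 85% in both arms, margin 0.10 and one-sided 5%: n = 2 × 0.85 × 0.15 × ((1.645 + 0.842)/0.10)² = 157.7, i.e. 158. Then 158/0.9 = 175.6, i.e. 176. Both reproduce. With 1.960 in place of 1.645 the result is 200.1, i.e. 201, so 158 implies a one-sided 5% test. The plan does not state the sidedness.

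**Assumptions for the illustration.** 176 per arm are randomised. True success among all randomised is 85% SPD and 75% SDD, exactly at the margin. Lost subjects who are not failures would have been successes. Noninferiority is declared if the lower one-sided 5% limit (unpooled) for SDD minus SPD lies above -10 points. All loss rates and failure shares are assumed, because the documents give none.

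**Formula.** Let p be true success, L the fraction lost and q the share of losses that are failures. Success among completers is (p - (1 - q)L)/(1 - L), so loss shifts an arm's rate by

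L × (q - (1 - p))/(1 - L).

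The SDD rate rises when q exceeds 0.25. The SPD rate rises when q exceeds 0.15 and falls when q is below it. The PP difference moves toward noninferiority when the SDD shift exceeds the SPD shift.

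**Same failure share in both arms** (errors by simulation, 4,000,000 trials per case; no loss gives 5.1%):

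| Loss SDD / SPD | q | SDD shift | SPD shift | PP difference (points) | False noninferiority |
|---|---|---|---|---|---|
| 5% / 3% | 0.5 | +1.32 | +1.08 | -9.77 | 5.8% |
| 12.5% / 7.5% | 0.5 | +3.57 | +2.84 | -9.27 | 7.4% |
| 5% / 0% | 0.5 | +1.32 | 0 | -8.68 | 9.3% |
| 5% / 3% | 0.25 | 0 | +0.31 | -10.31 | 4.4% |
| 12.5% / 7.5% | 0.25 | 0 | +0.81 | -10.81 | 3.5% |
| 5% / 0% | 0.25 | 0 | 0 | -10.00 | 5.1% |

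If every loss is a failure, an extreme case, the three loss patterns give 9.7%, 30% and 25%. Equal 10% loss, all failures, goes the other way: -11.1 points and 2.9%.

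**Different failure shares by arm** (2,000,000 trials per case):

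- Loss 10% in each arm, q = 0.5 SDD and 0.25 SPD. Shifts are 0.10 × 0.25/0.90 = +2.78 and 0.10 × 0.10/0.90 = +1.11 points. The difference is -8.33 points and the error 10.7%. A normal approximation agrees: SE = √(0.7778 × 0.2222/158.4 + 0.8611 × 0.1389/158.4) = 0.0430, and (0.0167/0.0430) - 1.645 = -1.26, i.e. about 10%.
- Loss 5% SDD (q = 0.5) and 10% SPD (q = 0.1). Shifts are +1.32 and -0.56. The difference is -8.13 points and the error about 11%.
- Loss none in SDD and 10% in SPD, all successes. The SPD shift is 0.10 × (-0.15)/0.90 = -1.67. The difference is -8.33 points and the error 10.3%, with no failure lost from either arm.

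So neither equal loss nor larger SPD loss rules out a shift toward noninferiority.

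**What an all-randomised analysis does.** Count preparation-related losses as failures and leave other losses missing. In the first unequal case SDD becomes 0.70/0.95 = 73.7% and SPD 0.775/0.925 = 83.8%, a difference of -10.1 points, so the shift is removed. In the second, error when both sets must pass is still about 7%. In the third the two sets are identical and error stays at 10.3%. A worst-case analysis (other losses as SDD failures and SPD successes) returns the third case to 75% against 0.75 + 0.10 = 85%.

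**The case against.** PP is a standard noninferiority analysis and often the more cautious one. The colonoscopists are blinded, cancelled subjects have no BBPS score, and the sample size already allows for 10% drop-out. The half-failure inflation is modest, and with a two-sided 95% interval it is only 3.0% to 5.2%, against 2.6% with no loss. The plan also names no confidence limit against the margin, only chi-square or Fisher tests at p < 0.05, so these error rates describe an inferred rule.

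Much of this stands. PP should stay, the size is uncertain, and the missing noninferiority test is a separate matter that adds no weight here. What does not follow is that PP alone suffices. Blinded scoring protects the scores that are obtained, not the choice of who is scored. The drop-out allowance preserves numbers, not comparability.

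Three stronger readings are tempting and not supported:

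- A reader might infer that the result is biased toward noninferiority. Without losses by arm and reason, even the direction is unknown.
- A reader might infer that examinations stopped for poor preparation were dropped. The text leaves this open and does not say so.
- A reader might infer that passing both sets holds the error at 5%. The second and third unequal cases show that it need not.

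**Conclusion.** The gap holds as a should-fix point: the only efficacy set is completers, some exclusions necessarily follow randomisation, and no all-randomised analysis is described. A PP-only result cannot show whether selective loss affected it.

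The size is conditional. Under the stated assumptions, including a one-sided 5% limit inferred from 158, plausible patterns leave the error near 5% or raise it to roughly 6% to 11%. Other patterns lower it. The figures of 25% and 30% need every loss to be a failure and should not be taken as typical. The sample size calculation itself is not in error.

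**What to change.** Keep PP and report beside it an analysis of all randomised subjects as assigned:

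- Count a colonoscopy not done or not completed for a preparation-related reason as a cleansing failure.
- Use the observed BBPS, where recorded, for wrong-time takers who were examined.
- Treat other losses as missing.
- State that examinations stopped for poor preparation stay in PP as failures.
- Add one worst-case sensitivity analysis: other losses as failures in SDD and successes in SPD. It is needed because the all-randomised set does not remove bias from losses unrelated to preparation. It is very strict and is for sensitivity only.
- Give losses by arm and reason, and interpret noninferiority by whether the sets agree, without claiming that passing both guarantees 5% error.

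The cost is one more analysis set and one sensitivity analysis from existing records, plus retrieval of cancellation reasons. No extra patients are needed. Enrolment ended in February 2018, so some reasons may be unobtainable; those subjects count as missing and the worst-case analysis covers them.

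Downsides to state:

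- With completers at 85% in both arms and 10% loss per arm, reported all-randomised success falls to 0.85 × 0.90 = 76.5% if all losses are failures, 0.765/0.95 = 80.5% if half, and 0.765/0.925 = 82.7% if a quarter.
- Power in that set is about 72%, 75% and 77% respectively, against 80% in PP.
- Wrong-time takers analysed as assigned mix the two regimens, which can itself favour noninferiority. This is a further reason to keep PP alongside.
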